10.7.1.1 Events of Interest (EOIs)

Events of interest of hypersensitivity and malignancy will be identified using a narrow search/scope in standardized MedDRA queries (SMQ). Event of interest of hypocalcemia, injection site reaction, hyperostosis, and osteoarthritis will be identified using Amgen-defined MedDRA search strategies. Subject incidence rates of these events will be provided.

Adjudicated positive cardiovascular serious adverse events, adjudicated AEs of osteonecrosis of the jaw (ONJ) and atypical femoral fracture (AFF) will also be summarized as EOIs.

10.7.1.1.1 Osteonecrosis of the Jaw Adjudication

The events of ONJ which occurred in the study will be adjudicated and summarized. All potential events of ONJ identified through a pre-defined search of the MedDRA terms will be submitted to the ONJ Adjudication committee for review and adjudication. The committee will determine whether the event meets the case definition criteria for ONJ.

Number of adjudicated positive ONJ events will be summarized.

10.7.1.1.2 Atypical Femoral Fracture Adjudication

The events of AFF which occurred in the study will be adjudicated and summarized. All potential events of AFF identified through a pre-defined search of the MedDRA terms will be submitted to the AFF Adjudication committee for review and adjudication. The committee will determine whether the event meets the case definition criteria for AFF.

Number of adjudicated positive AFF events will be summarized.

10.7.1.1.3 Injection Site Reaction

The duration, severity and nature (concomitant, recurrent) of the injection site reactions will be summarized. The time (in days) to first injection site reaction will also be summarized descriptively.

10.7.1.1.4 Adjudicated Positive Serious Cardiovascular Events

All deaths and potential cardiovascular-related serious AEs will be submitted to an external independent committee comprised of experienced cardiologists for adjudication. The committee will adjudicate the events and determine whether the event is cardiovascular in nature.

Only events confirmed positive by the adjudication committee to meet cardiovascular event definition criteria will be included for analysis. Adjudicated cardiovascular events of death, cardiac ischemic event, cerebrovascular event, non-coronary revascularization, heart failure and peripheral vascular events not requiring revascularization will be summarized using subject incidence rates. No statistical tests will be performed

10.7.2 Laboratory Test Results

The analyses of safety laboratory endpoints will include summary statistics (absolute value, change from baseline and percent change from baseline) over time by visit for the 6-month treatment period for selected analytes (hemoglobin, lymphocytes, total neutrophils, white blood cell, phosphorus, alkaline phosphatase, calcium corrected by albumin, magnesium, glucose, alanine amino transferase [ALT], aspartate amino transferase [AST], eosinophil, total bilirubin, and creatinine). Of note, these summaries will also be provided in conventional units for: hemoglobin, phosphorus, magnesium, total bilirubin, creatinine and calcium corrected by albumin.

Laboratory shift tables based on Common Terminology Criteria for Adverse Events v3.0 (CTCAE) will also be provided to compare baseline laboratory values with the most extreme post-baseline values through 6 months. Subject incidence of worst

post-baseline calcium corrected by albumin CTCAE grades decreases will also be summarized. The percentages of subjects with laboratory toxicities \geq grade 3 CTCAE will be summarized.

Graphs showing central tendency and dispersion of the absolute values and percent changes from baseline by visit will also be provided for the following laboratory parameters: calcium corrected by albumin, phosphorus and alkaline phosphatase.

Drug-induced liver injury will be assessed by evaluating subjects for Hy's Law. Hy's law laboratory criteria are defined as AST or ALT $>$ 3 times upper limit of normal (ULN), total bilirubin $>$ 2 times ULN, and alkaline phosphatase $<$ 2 times ULN assessed within 7 days. Subjects who meet these Hy's law laboratory criteria on study will be further evaluated to assess whether there exist underlying conditions or concomitant medications which can explain the elevation in laboratory analytes in order to assess whether these cases are true Hy's law cases.

All these analyses will be performed using the safety analysis set.

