6.3 Hepatotoxicity Stopping and Rechallenge Rules

Subjects with abnormal hepatic laboratory values (ie, alkaline phosphatase [ALP], aspartate aminotransferase [AST], alanine aminotransferase [ALT], total bilirubin [TBL]) and/or international normalized ratio [INR] and/or signs/symptoms of hepatitis (as described below) may meet the criteria for withholding or permanent discontinuation of Amgen IP or other protocol-required therapies as specified in the [Guidance for Industry Drug-Induced Liver Injury \(DILI\): Premarketing Clinical Evaluation, July 2009](#)).

6.3.1 Criteria for Permanent Discontinuation of Amgen Investigational Product and Other Protocol-required Therapies due to Potential Hepatotoxicity

Amgen IP (romosozumab/placebo) should be discontinued permanently and the subject should be followed according to the recommendations in [Appendix A](#) (Additional Safety Assessment Information) for possible DILI, if ALL of the criteria below are met:

- TBL > 2x ULN or INR > 1.5
- AND increased AST or ALT from the relevant baseline value as specified below:

Baseline AST or ALT value	AST or ALT elevation
< ULN	> 3x ULN

- AND no other cause for the combination of the above laboratory abnormalities is immediately apparent; important alternative causes for elevated AST/ALT and/or TBL values include, but are not limited to:
 - Hepatobiliary tract disease
 - Viral hepatitis (eg, Hepatitis A/B/C/D/E, Epstein-Barr Virus, cytomegalovirus, Herpes Simplex Virus, Varicella, toxoplasmosis, and Parvovirus)

- Right sided heart failure, hypotension or any cause of hypoxia to the liver causing ischemia
- Exposure to hepatotoxic agents/drugs or hepatotoxins, including herbal and dietary supplements, plants and mushrooms
- Heritable disorders causing impaired glucuronidation (eg, Gilbert’s Syndrome, Crigler-Najjar syndrome) and drugs that inhibit bilirubin glucuronidation (eg, indinavir, atazanavir)
- Alpha-one antitrypsin deficiency
- Alcoholic hepatitis
- Autoimmune hepatitis
- Wilson’s disease and hemochromatosis
- Nonalcoholic Fatty Liver Disease including Steatohepatitis
- Non-hepatic causes (eg, rhabdomyolysis, hemolysis)

6.3.2 Criteria for Conditional Withholding of Amgen Investigational Product and Other Protocol-required Therapies due to Potential Hepatotoxicity

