ALP = alkaline phosphatase; ALT (SGPT) = alanine aminotransferase (serum glutamic pyruvic transaminase); AST (SGOT) = aspartate aminotransferase (serum glutamic oxaloacetic transaminase); BTM = bone turnover marker; HepBsAg = hepatitis B surface antigen; HepBcAb = total hepatitis B core antibody; iPTH = intact-parathyroid hormone; T4 = thyroxine; TBL = total bilirubin; TSH=thyroid stimulating hormone.

^a Results of post-day 1 assessments will be blinded to any study-related personnel (including the sites) except for serum calcium, albumin-adjusted calcium, phosphorus, or ALP in the event of a panic value.

Results of laboratory assessments for serum calcium, albumin-adjusted calcium, phosphorus, ALP, P1NP, CTX, iPTH, romosozumab levels, and anti-romosozumab antibodies are considered potentially unblinding and will not be reported to any study-related personnel after day 1 in order to maintain the integrity of the study blind. However, in the event of an abnormal value of clinical relevance (panic value) for serum calcium, albumin-adjusted calcium, phosphorus, or ALP, sites will be notified of the unblinded value by the central laboratory. After such notification is issued, the sites may perform additional follow-up blood draws for local analysis as required to support subject medical care. Notifications will also be issued for subjects who test positive for neutralizing anti-romosozumab antibodies at the final scheduled study visit (refer to [Section 7.3](#) for details).

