10.5.5.1 Adverse Events

For the 6-month treatment period, subject incidence of all treatment-emergent adverse events will be tabulated by system organ class and preferred term. Tables of fatal adverse events, serious adverse events, **events of interest (including positively adjudicated osteonecrosis of the jaw, positively adjudicated atypical femoral fracture, injection site reaction, and positively adjudicated serious cardiovascular adverse events)**, adverse events leading to withdrawal from IP or other

protocol-required therapies, and treatment-emergent adverse events will also be provided. Subject incidence of disease-related events and fatal disease-related events will be tabulated by system organ class and preferred term. The treatment-emergent adverse events in the overall 9-month study period (6-month treatment period followed by a 3-month follow-up period) will be summarized using the same approach as for the 6-month treatment period. In addition, adverse events reported between month 6 and month 9 (no treatment phase) will be listed by subject number and treatment received in the first 6 months.

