10.5.5.3 Laboratory Assessments

The analyses of safety laboratory endpoints will include summary statistics (actual value and change or percent change from baseline for each laboratory parameter) over time by visit for the 6-month treatment period. Shifts in grades of safety laboratory values between the baseline and the worst on-study value will be tabulated. Graphical representation of aggregate data may also be presented.

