10.7.1 Adverse Events

The Medical Dictionary for Regulatory Activities (MedDRA) version 20.0 or later will be used to code all AEs to a system organ class and a preferred term. AEs will be summarized in the 6-month treatment period and in the 9-month study period for all subjects who receive at least one dose of IP in the treatment period, ie, safety analysis

set. The subject incidence rates for the 9-month study period will include all events that occurred in the 6-month treatment period, and in addition, all events that occurred in the additional 3 month follow-up period. In addition, AEs reported between month 6 and month 9 (no treatment phase) will be listed by subject number and treatment received in the first 6 months.

All AE tables will be summarized by treatment group. The subject incidence of AEs will be summarized for all treatment emergent, serious, treatment related, serious treatment related, leading to withdrawal of IP, fatal, and of special interest. Subject incidence of special interest adverse events will also be summarized according to their categories.

Subject incidence of all treatment emergent, , serious, those leading to withdrawal of IP, related to IP adverse events will be tabulated by system organ class (SOC) and preferred term in descending order of frequency in the romosozumab arm. Fatal adverse events will be tabulated by preferred term in descending order of frequency in the romosozumab arm.

Disease related events (DRE) will be indicated in the AE listing and only tabulated with sufficient data.

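### SAP limits by-visit laboratory summaries to 14 of 28 chemistry and hematology parameters and drops non-IP therapies from the AE-withdrawal table

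*SAP*

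**What the plan says.** **Laboratory summaries.** Protocol Section 10.5.5.3 plans "summary statistics (actual value and change or percent change from baseline for each laboratory parameter) over time by visit for the 6-month treatment period". The endpoint itself (Protocol Section 10.1.1.4, repeated in SAP Section 4.1.4) has two parts, change from baseline and shift to the worst value, both for serum chemistry and hematology as a whole. SAP Section 10.7.2 then provides the summary statistics "over time by visit for the 6-month treatment period for selected analytes" and names 14. The same section adds CTCAE shift tables and the percentage of subjects with grade 3 or higher toxicities, without tying either to the named analytes.

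**AE withdrawals.** Protocol Section 10.5.5.1 lists a table of "adverse events leading to withdrawal from IP or other" protocol-required therapies. SAP Section 10.7.1 lists withdrawal of IP in its overall summary, and for the detailed tables says "those leading to withdrawal of IP, related to IP adverse events will be tabulated by system organ class" and preferred term. Neither statement mentions the other therapies.

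**Liver.** SAP Section 10.7.2 also states "Drug-induced liver injury will be assessed by evaluating subjects for" Hy's law: AST or ALT above 3x ULN, total bilirubin above 2x ULN and alkaline phosphatase (ALP) below 2x ULN within 7 days. Protocol Section 6.3.1 combines an AST or ALT rise with "TBL > 2x ULN or INR > 1.5", requires that no other cause be apparent, and sets no ALP condition.

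In the copy supplied, SAP Section 11 (changes from protocol-specified analyses) shows a heading and no text.

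**The concern.** The SAP should carry out what the protocol promises or record where it departs. Here it appears to do neither for two safety outputs. For the laboratory endpoint, the SAP's method is also narrower than its own endpoint definition. A programmer working from SAP Section 10.7.2 would produce no by-visit mean or change for sodium, potassium, albumin, urea nitrogen, red cells or platelets, among others.

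For withdrawals, the therapies left out are calcium and vitamin D. Protocol Section 2.3 treats them as necessary alongside romosozumab, and Protocol Section 6.2.2.3 foresees changes to them for hypercalcemia or intolerance. A reader of the study report could not see how often an AE led a subject to stop them.

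The liver definitions raise a lesser question. A subject who meets the protocol's laboratory limbs for potential liver injury could be missing from the SAP's liver assessment.

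**Working it through.** No figure in the plan is being reproduced; the check is a count and a comparison of text.

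**1. Laboratory parameters (Protocol Table 2 against SAP Section 10.7.2).** The differential is counted by its five cell types, not as an item of its own.

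| Panel | In Table 2 | Named in SAP | Not named |
|---|---|---|---|
| Serum chemistry | 19 | 9 | 10 |
| Hematology | 9 | 5 | 4 |
| Total | 28 | 14 | 14 |

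- Named, chemistry: phosphorus, ALP, albumin-adjusted calcium, magnesium, glucose, ALT, AST, total bilirubin, creatinine.
- Named, hematology: hemoglobin, lymphocytes, neutrophils, white cells, eosinophils.
- Not named, chemistry: sodium, potassium, chloride, bicarbonate, total protein, albumin, unadjusted calcium, urea nitrogen, TSH, free T4.
- Not named, hematology: red cells, platelets, basophils, monocytes.

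All 14 named analytes are in Table 2. Share without by-visit summaries: 14 / 28 = 50%. If TSH and free T4 are set aside as screening-type tests, which is an assumption, the share is 12 / 26 = 46%.

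**2. What remains for the 14 not named.** The shift tables and the grade 3 or higher summary can include any analyte with a CTCAE grade. The documents do not show which of the 14 have one. An analyte without a grade may have no output.

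**3. AE withdrawals.** Protocol category: IP, or other required therapies. SAP category: IP. The difference is AEs that led to stopping calcium or vitamin D but not IP. These still count in the all-AE tables; what is lost is the separate category.

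**4. Liver definitions.** Two illustrative subjects, each with baseline AST and ALT below ULN and values on the same day:

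| Values | Protocol 6.3.1 laboratory limbs | SAP Hy's law |
|---|---|---|
| ALT 4x ULN, bilirubin 2.5x ULN, ALP 2.2x ULN | Met | Not met (ALP) |
| ALT 4x ULN, bilirubin 1.5x ULN, INR 1.8 | Met (INR) | Not met (bilirubin) |

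The table covers the laboratory limbs only; Section 6.3.1 also requires that no alternative cause be apparent. INR is not in Table 2. The documents call for it only in the Appendix A work-up, so an INR limb can be assessed only in subjects who had that work-up.

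**The case against.** The strongest reply is that little is lost. Safety is descriptive, with no inferential testing, in about 60 subjects. Calcium or vitamin D intolerance can be handled by changing the formulation or dose, so few AE withdrawals from them are likely. No efficacy conclusion depends on any of this. That stands, and it keeps the point modest. It does not remove it: a grade shift is not a change from baseline, and the endpoint names both.

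Three stronger readings are tempting, and the documents do not support them.

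- A reader might infer that the omitted items get no analysis. The unrestricted shift and grade 3 or higher outputs can cover laboratory parameters, the all-AE tables cover the withdrawal AEs, and Protocol Appendix A makes potential liver-injury cases reportable as SAEs, so they enter the SAE tables.
- A reader might infer that the SAP's safety outputs are narrower in general. The SAP adds events of interest for hypersensitivity, malignancy, hypocalcemia, hyperostosis and osteoarthritis, as well as body weight, BMI and the Hy's law review. Protocol Section 10.5.5 plans no liver-injury output, and Section 6.3.1 is a stopping rule that also triggers reporting. On the liver, the SAP adds an output with a different case definition; it does not cut one.
- A reader might infer that the ALP condition removes cases unequally by arm. Protocol Section 7.4 says only that ALP and other results "are considered potentially unblinding and will not be reported to any study-related personnel after day 1". Neither document gives the direction or size of any ALP change, or suggests values near 2x ULN.

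**Conclusion.** The point holds for two outputs. By-visit change-from-baseline summaries are missing for 14 of 28 chemistry and hematology parameters (12 of 26 if the thyroid tests are set aside), against both the protocol and the SAP's own endpoint. The AE-withdrawal table omits therapies that the protocol includes. Neither departure is explained in the copy supplied. The conclusion rests on reading the SAP's 14 names as a complete list, which its wording supports.

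The difference in liver definition is real but secondary. It justifies an optional supplementary count, not a claim that a planned analysis was dropped.

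**What to change.** - **SAP Section 10.7.2:** produce the by-visit summaries (value, change and percent change from baseline) for all chemistry and hematology parameters measured on study.
- **SAP Section 10.7.1:** define the withdrawal category as AEs causing withdrawal of IP or of any other required therapy, in both the overall summary and the detailed table.
- **Optional, SAP Section 10.7.2:** count subjects with (AST or ALT above 3x ULN) and total bilirubin above 2x ULN within the same 7-day window, regardless of ALP, and show Hy's law as a labelled subset. List INR-based cases only where INR was drawn. This concerns the summary table alone and leaves the stopping rule in Protocol Section 6.3.1 untouched.

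If the sponsor prefers to keep either restriction, SAP Section 11 should record it with a reason.

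The cost is a few extra standard tables from data already collected. For the withdrawal table this assumes that the action-taken item required for each AE (Protocol Section 9.2.2.1) identifies calcium and vitamin D; their stop dates are recorded under Protocol Section 6.2.2.

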10.7.3 Vital Signs, Body Weight, and BMI

Descriptive statistics of actual values and changes from baseline in vital signs (systolic and diastolic blood pressure, heart rate, and temperature), body weight, and BMI will be presented by scheduled visit. These analyses will be performed using the safety analysis set.

10.7.4 Antibody Formation

The incidence and percentage of subjects who develop anti-romosozumab antibodies (binding, and if positive, neutralizing) at months 1, 3, and 6 will be tabulated by treatment group for primary analysis **and repeated for the final analysis to include all testing results from samples collected during the 3-month follow-up period (at month 9)**.

For subjects who develop anti-romosozumab antibodies, romosozumab serum concentrations may also be analyzed. Subjects who test positive for binding antibodies against romosozumab will be interpreted as transient positive if the binding antibody status was negative at the subject's last time point tested within the study period. Subjects who test positive for neutralizing antibodies against romosozumab will be interpreted as transient positive if the neutralizing antibody status was negative at the subject's last time point tested within study period.

10.7.5 Exposure to Investigational Product

Descriptive statistics will be produced to describe the exposure to IP by randomized treatment group. The number of days on study, the number of doses received, and the cumulative exposure to IP will be summarized using the full analysis set.

10.8 Pharmacokinetic Analyses

Individual and mean serum romosozumab concentration-time data will be tabulated and presented graphically using nominal times. Descriptive statistics will be provided for romosozumab serum concentrations at each time point. The data set will be analyzed using the current version of Phoenix WinNonlin within the Pharsight Knowledgebase System (PKS) data repository. Romosozumab serum concentrations with values below the lower limit of quantification will be set to zero for analysis. Reasons for excluding any data from the PK analyses will be provided. These analyses will be performed by the **CPMS** group.

11. Changes From Protocol-specified Analyses

12. Literature Citations / References

13. Appendices

13.1 Technical Detail and Supplemental Information Regarding Statistical Procedures and Programs

13.1.1 Dates

All dates should be converted to SAS dates prior to their use in any calculation.

13.1.2 Analysis Visit Windows

For the baseline assessment (excluding DXA), regardless of the width of the visit window, if there are multiple records within a Baseline window, the record that is the closest to and on or prior to Study Day 1 will be considered as the baseline value.

For the post-baseline assessment, if more than 1 visit falls within the defined window, the result from the visit closest to the target day will be used. If 2 evaluations are of the same distance from the target day, the result from the later visit will be used.

To allow for variations in scheduling, the following visit windows will be used to assign evaluations to a most appropriate nominal visit for analysis and summarization.

Furthermore, there will be no gaps between visit windows in order to include as many data points as possible for summarization.

Spine and Hip DXA Scans

Nominal Visit	Target Day	Window Definition (Study Day)
Baseline ^a	1	Last evaluation prior to or on Study Day 1
Month 6	183	≥ Study Day 2

^a If results from baseline DXA are not available, the results from scans taken on or before Study Day 14 will be considered baseline values and not the Month 6 values.

Serum Romosozumab Levels and BTMs (serum CTX and P1NP) and Laboratory Assessments

Nominal Visit	Target Day	Window Definition (Study Day)
Baseline	1	Last evaluation prior to or on Study Day 1
Month 1	31	Study Day 2 to 61
Month 3	92	Study Day 62 to 137
Month 6	183	≥ Study Day 138

[figure not shown]
Vital Signs

Nominal Visit	Target Day	Window Definition (Study Day)
Baseline	1	Last evaluation prior to or on Study Day 1
Month 1	31	Study Day 2 to 61
Month 6	183	≥ Study Day 62

Antibody Assessments

Nominal Visit	Target Day	Window Definition (Study Day)
Baseline	1	Last evaluation prior to or on Study Day 1
Month 1	31	Study Day 2 to 61
Month 3	92	Study Day 62 to 137
Month 6	183	Study Day 138 to 229
Month 9	275	≥ 229

CCI

CCI

